We hypothesize that Myrbetriq™, as a $\beta(3)$ -AR agonist⁶, could harbor a great therapeutic potential for controlling storage bladder symptoms (LUTS) and ureteral pain associated with ureteral stent placement.

Study Objective and Endpoints

The objective of this pilot study is to assess whether Myrbetriq™ will improve post-operative ureteral pain and discomfort, reduce bladder storage symptoms and increase quality of life following ureteral stenting. This study will be conducted as an exploratory pilot investigation. In doing so, we will confirm the potential effect size for reduction in associated pain following stenting within this study population. Results from this pilot study will also be used to assess feasibility for the design and conduct of a larger, prospective study in this population.

Primary Endpoints:

- Improvement from baseline in the Incontinence Symptom Severity Index (ISSI) in the Myrbetriq™ group at the 1 week follow-up and 2 week follow-up compared to placebo group.
- Improvement from baseline in the number micturition per 24 hours and the number of incontinence episodes in the Myrbetriq™ group at the 1 week follow-up and 2 week follow-up compared to placebo group.

Exploratory Endpoints:

- Improvement in pain and discomfort perception using a 10 point Visual Analog Scale for pain assessment (VAS) at the 1 and 2 week follow-up.
- Improvement from baseline on the Patient Global Impression of Severity (PGI-S) at the 2 week follow-up.

- Reduction in pain medicine intake at the 2 week follow-up.

Study Methods

This study is a prospective, randomized, double-blind, placebo-controlled 2 week clinical trial to evaluate the efficacy of Myrbetriq™ to reduce ureteral stent related pain and bladder symptoms in subjects undergoing a urologic procedure involving ureteral stenting. The study will be conducted at Southern Illinois University (SIU) School of Medicine, Department of Urology and its affiliated hospitals in Springfield, IL.

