Data analysis will be concluded upon the completion of the study. Subjects' age, height, weight, and other continuous baseline variables will be summarized using descriptive statistics, while gender, race and other categorical variables will be provided using frequency tabulations. Medical history data will be summarized using frequency tabulations by system organ class and preferred term. Chi-square and t-tests will be used, as appropriate, to compare percent change and mean change from baseline in the ISSI, voiding diary, narcotic log, VAS score and PGI-S at the final study visit (14 days) or at any early termination visit. A split-plot ANOVA with repeated measures will be used for each measure (ISSI, VAS and PGI-S) to compare groups (Myrbetriq™ and placebo) over time and to determine if there is an interaction between groups. Significance will be assumed when $p < 0.05$. A preliminary power analysis based on previously published data, using an estimated SD for each study group of 4.17, a sample size of 50 in each study group (Myrbetriq™ and placebo) has an 80% power to detect an ISSI difference of 25% between the two groups with a significance level (alpha) of 0.05 (two-tailed)¹².

Pertinent to each Specific Aim are the following calculations:

- Primary Endpoints: Comparison of the change from baseline in ISSI and voiding diaries between Myrbetriq™ and placebo will be made using an independent t test for continuous scoring and a chi-squared test for ordinal scoring. Inferential analyses of changes from base line in micturition episodes per 24 hours and incontinence episodes per 24 hours will be performed using a stratified rank analysis to compare to baseline and as a covariance for each treatment.
- Exploratory Endpoints: Comparison of the change from baseline of total VAS between Myrbetriq™ and placebo will be made using an independent t test for continuous scoring and a chi-squared test for ordinal scoring. Comparison of the change from baseline in PGI-S between Myrbetriq™ and placebo will be made using an independent t test for

continuous scoring and a chi-squared test for ordinal scoring. Comparison of pain medicine intake between Myrbetriq™ and placebo groups will be made using an independent t test.

Safety Considerations

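### The inferential analysis of the two diary primary endpoints names no drug-versus-placebo contrast and has undefined strata, and a between-arm t or chi-squared test covers the same data with neither said to decide

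*Combined protocol and SAP*

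**What the plan says.** Under Study Objective and Endpoints, the second primary endpoint is "Improvement from baseline in the number micturition per 24 hours and the number of incontinence episodes in the" active group, "at the 1 week follow-up and 2 week follow-up compared to placebo group". The intended contrast is between arms.

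Three statements under Statistical Analyses cover the diary:

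- The general paragraph: "Chi-square and t-tests will be used, as appropriate, to compare percent change and mean change from baseline in the ISSI, voiding diary" and other measures, at the final or early termination visit.
- The Primary Endpoints bullet, first sentence: "Comparison of the change from baseline in ISSI and voiding diaries between Myrbetriq™ and placebo will be made using an independent t test", with a chi-squared test where scoring is ordinal.
- The same bullet, second sentence: the inferential analysis of change in the two counts is described as "performed using a stratified rank analysis to compare to baseline and as a covariance for each treatment".

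The last is the only one of the three that is labelled inferential and the only one that names the two counts. The section sets significance at p < 0.05 and gives no order among these analyses. Randomization Schema describes a simple random numbers table and no stratification factor. Study Methods obtains the baseline diary 14 days after stent removal, and the schedule of assessments shows no diary at the baseline visit.

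**The concern.** Read literally, the inferential sentence compares each arm with its own baseline. Change within an arm mixes any drug effect with the course of the stent, recovery from surgery and placebo response, and it makes no use of the randomised control. A significant change in one arm beside a non-significant change in the other could then be taken for efficacy when the arms do not differ.

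If the sentence instead means a rank ANCOVA, it still leaves out the treatment contrast, the role of baseline and the strata, so an analyst could not run it from the text. On either reading, a t or chi-squared test competes for the same primary data, and the more favourable result could be reported.

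**Working it through.** **The plan's own figure.** The only power statement concerns the ISSI: 50 per arm, SD 4.17, two-sided 0.05, 80% power. The detectable difference is (1.960 + 0.842) × 4.17 × √(2/50) = 2.34 points. That equals 25% only if the reference mean is 2.34/0.25, about 9.35, which is not given. No power or error figure is stated for the diary counts, so there is nothing to reproduce for this point.

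**The texts side by side.**

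| Element | Endpoint definition | t / chi-squared sentence | Rank sentence |
|---|---|---|---|
| Contrast | drug vs placebo | drug vs placebo | with baseline, for each treatment |
| Measure | the two counts, change from baseline | change in diaries | the two counts, change from baseline |
| Time | weeks 1 and 2 | not stated | not stated |
| Strata | none | none | stratified, factor not named |
| Decides? | – | not stated | not stated, but labelled inferential |

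**Consequence of the within-arm reading.** Inputs: n = 50 per arm and two-sided 0.05, both from Statistical Analyses. Assumption: both arms change by the same true amount δ, in SDs of the change, so there is no drug effect. The documents give no value for δ, so a range is shown.

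The rejection probability p in one arm comes from the noncentral t with 49 degrees of freedom and noncentrality δ√50. For example, δ = 0.2 gives noncentrality 1.41 and p = 28%. The arms are independent, so drug significant and placebo not has probability p(1 − p).

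| δ | p, drug arm alone | p(1 − p) |
|---|---|---|
| 0.1 | 10.7% | 9.5% |
| 0.2 | 28.3% | 20.3% |
| 0.28 | 49.2% | 25.0% |
| 0.4 | 79.2% | 16.5% |
| 0.5 | 93.4% | 6.2% |
| 0.8 | nearly 100% | about 0% |

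p(1 − p) cannot exceed 25%, which it reaches at p = 50%. A simulation with Wilcoxon signed-rank tests (4,000 trials, normal changes) agrees. The drug arm rejected in 28%, 77% and 93% of trials at 0.2, 0.4 and 0.5 SD, and the discordant pattern occurred in 20.5%, 16.9% and 7.7%. Between-arm t and rank tests stayed at about 4.5% to 5.5% at every δ.

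**Consequence of two unranked between-arm tests.** In the same simulation, counting either the t or the Mann-Whitney test as a success gave 5.6% to 6.6% for normal changes. For one assumed skewed count (negative binomial, size 0.5, probability 0.3, at both times) it gave 7.2%. The Monte Carlo standard error is about √(0.06 × 0.94/4000) = 0.4 points, so roughly 5.5% to 7.5% is a fair range.

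**The case against.** The strongest reply is that the sentence was never meant as a within-arm test. The reference to covariance suggests baseline as a covariate in a stratified rank ANCOVA that compares treatments. That may well be so, and it rules out saying that a within-arm test is planned. It does not rescue the sentence, which still lacks the contrast and the strata. The covariate would also be a diary collected after randomisation and after stent removal.

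Second, a drug-versus-placebo comparison of the diary is in the plan, in the sentence just before. This is correct. A reader might infer that the placebo comparison is missing altogether, and the documents do not support that. What is missing is any statement of which analysis decides.

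Third, a reader might take 17% to 25% as this trial's false-positive rate. The documents do not support that either. The plan contains no rule of drug significant and placebo not, and the figure is the peak of an assumed range. With the late baseline diary, a within-arm contrast would set stented against stent-free time. The documents do not size that shift. If it is large, the discordant pattern almost disappears, although each arm alone would then nearly always be significant.

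Fourth, a reader might infer a larger inflation by adding the chi-squared test. The plan keeps that test for ordinal scoring and describes no grouping of the counts, so it is not counted here.

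Finally, the study is an exploratory pilot with mainly descriptive statistics. That lowers the stakes. But the plan names these endpoints as primary, sets p < 0.05, and intends the results to inform a larger study.

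**Conclusion.** The point stands as a defect of specification with a practical consequence: the wording would let a within-arm result, or the better of two between-arm tests, settle a primary endpoint defined against placebo. The size depends on the reading:

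- **Within-arm reading:** the drug-versus-placebo error is not controlled. Rejection in the drug arm alone is about 28% to 79% at an assumed common change of 0.2 to 0.4 SD. The discordant pattern is at most about 25%, about 10% at 0.1 SD, 6% at 0.5 SD and near 0 at 0.8 SD.
- **Choice between the between-arm t and rank tests:** the excess is small, with total error roughly 5.5% to 7.5% depending on the distribution.

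These figures assume 50 analysed per arm, no drug effect and, for the within-arm table, normal changes. The textual finding needs none of these assumptions. The plan should be corrected, but the fault does not undermine the trial's design.

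**What to change.** For the diary counts, replace the two sentences of the Primary Endpoints bullet with one statement:

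- One deciding rank test of drug against placebo for each count (micturitions and incontinence episodes per 24 hours) at each stated time point, week 1 and week 2, with the between-arm difference and its 95% CI.
- The t and chi-squared tests are supportive only, including where the general paragraph lists the voiding diary.
- Delete the word stratified, or name the strata.
- Report within-arm change without p-values.
- Compare the week-1 and week-2 counts directly. Because the baseline diary is obtained 14 days after stent removal, do not use it as a covariate or as the basis of the deciding test. Report change from it descriptively.

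The cost is a rewording, with no change to sample size, visits or data collection. The downside is that the change-from-baseline form of this endpoint becomes descriptive for the diary counts, so the endpoint definition should be aligned. The repair leaves four tests (two counts at two times), and any adjustment across them is a separate decision.

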Subjects will be enrolled per the inclusion/exclusion criteria. Subjects will be screened and consented prior to their stent placement procedure for stone disease. Patients will be formally enrolled and randomized post-operatively based on no severe complications intra-operatively, such as extensive extravasation, hematoma could confound the pain and compromise the results. All subjects will complete at baseline and all follow-up visits: 1) the Incontinence Symptoms Severity Index (ISSI), 2) American Urologic Association symptom score (AUASS) 3) the Visual Analog Scale (VAS) to represent change in acute pain 4) the Patient Global Impression of Severity (PGI-S) quality of life scale 5) a voiding diary for 1 to 3 days preceding day, 7, and stent removal visits, and then 14 days after the stent removal (if done by day 28) to obtain base line diary and 6) a narcotic log starting after surgery through 14 days after stent removal (if done by day 28). The ISSI will be used to assess any change in voiding symptoms. This scale has been validated to efficiently capture and quantify urological symptoms⁷. The voiding diary is used to capture the number of micturition per day, urgency and associated incontinence. The VAS has been validated to measure changes in acute pain that are clinically significant⁸. The PGI-S has been proven to efficiently summarize a patient's perception to change in severity in regards to lower urinary tract symptoms (LUTS)⁹. Subjects will undergo a blood draw prior to stent placement (complete blood count (CBC), comprehensive metabolic panel (CMP) and urine analysis (sugar, protein, WBC/RBC, bacteria)) to verify eligibility. These laboratories will not be repeated if they were performed routinely as a part of preoperative work up. 100 subjects will be equally randomized into 1 of 2 study groups, active treatment with Myrbetriq™ or administration of a placebo. A daily 50 mg dose of Myrbetriq™ will be administered in the treatment group for up to 4 weeks initiated on the day of stent placement. A 50mg dose was chosen as the initial dose due to the acute nature of the symptoms which do not require long term therapy. It has been shown that Myrbetriq™ 50 mg taken orally once daily has superior efficacy in treatment of LUTS when compared to placebo by week 4 (the duration of this study) and this effect was maintained. A 50mg dose was proven to be safe and effective to patients in Phase III trials^{10,11}. Both study groups will receive similar prescriptions of narcotics in dose and number. Patients will be given a log to record use of narcotics. If a different form of narcotics is prescribed due to side effects or allergic reaction, a narcotic analgesia converter calculator will be used to adjust for the doses, for analysis purposes. Post-operative symptoms and pain medicine intake will be assessed at days 1, 7 via telephone interview, and with a clinic visit the day of stent removal (or day 14 if stent removal postponed) and via phone 14 days after the stent is removed. If patient is to have stent removed on day 28, or later, the patient will receive a day 21 telephone call to obtain post-operative pain and pain medicine intake, as well as questionnaires. They will remain on study drug until day 28. Use of prescription, over-the-counter and supplemental medications for pain control will be captured using self-report and direct observation/recording of medication labels by the study team. These interviews will be conducted by study staff who will be blinded to the subject's treatment. Subjects will complete

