
the ISSI, the AUASS, voiding diary, VAS, narcotic log, and PGI-S during these follow ups. The day 14 assessments will be collected prior to their stent removal procedure.

Study Subjects

Patients will be identified and recruited through the SIU urology clinics and St. John's Hospital during a 24 month enrollment period. Participation in this study will be completely voluntary. Male and female subjects presenting with planned stent placement for ureteral obstruction or post-ureteroscopy procedures for stone, except for those undergoing uteropelvic junction obstruction, will be evaluated for participation. Should the patient decline to participate, their choice will not change their prescribed course of standard urologic treatment. After review and approval by the local Institutional Review Board, the study will enroll 100 patients that meet the inclusion criteria below and agree to participate. Annually, the study investigators perform approximately 350 stenting procedures (based on 2 previous years of clinical data).

Inclusion Criteria

1. Age \geq 18.
2. Subject scheduled to undergo a ureteral stent placement for ureteral obstruction or post-ureteroscopy procedure.
3. Otherwise healthy subjects who are able and willing to participate in the study.
4. None of the planned interventions are documented in the labeled contraindications, warnings and precautions of the study drug.

Exclusion Criteria

1. Does NOT give consent.
2. Subject is using prohibited medications which cannot be stopped safely at the screening visit. Subject is excluded if using restricted medications not meeting protocol-specified criteria:
 - (i) Phytotherapy for BPH or a 5-alpha reductase inhibitor within 3 months, with persistent urinary symptoms and AUASS more than 7.
 - (ii) Taken an oral alpha agonist, anticholinergic or cholinergic medication within 5 days of the first screening visit with the following exception(s): a singular dose given in ER or on the hospital floor prior to procedure, topical anticholinergic eye drops used for glaucoma or inhaled anti-cholinergic used for COPD.
 - (iii) Taken tricyclic antidepressants within 2 weeks of the first screening visit.
 - (iv) Taken an estrogen, androgen, or any drug producing androgen suppression, or anabolic steroids within 3 months with the following exceptions: any topical creams for local treatment.
3. Post void residual volume $>$ 350 mL.

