19. Unable to follow protocol directions due to organic brain or psychiatric disease.
20. Intra-operative complications that require hospital admissions.
21. History of alcoholism or any other substance abuse, which, in the opinion of the investigator, would affect compliance with the protocol.

Assessment or Procedure	Baseline/ Stent Placement	Post-Op Day 1 (phone)	Post-Op Day 7 (phone)	Stent removal (Post-Op Day 14 if stent not removed) visit	Post- Op Day 21 (phone) (if stent not removed)	2 weeks after stent removal or Day 42 (phone)	Early Withdrawal
Informed Consent	X						
Verify Eligibility	X						
Review Medical & Surgical History	X						
Physical Examination (H & P)	X			BP and HR only			BP and HR only
Review Prior & Current Medications	X	X	X	X	X	X	X
Review Adverse Events		X	X	X	X	X	X
ISSI	X	X	X	X	X	X	X
VAS	X	X	X	X	X	X	X
PGI-S Quality of Life Scale	X	X	X	X	X	X	X
AUASS	X	X	X	X	X	X	X
Voiding diary			X	X		X	
Pain log		X	X	X	X	X	X
Laboratory screening tests (hematology & chemistry)	X						
Randomization	X						
Study drug administration/Accountability	X			X		X only if you have drug	X

Visit window for all visits are +/- 2 days

Study Procedures

Informed Consent

All participants will be required to provide written informed consent. The study staff will introduce the study after being informed the subject is potentially eligible. The study coordinator and/or study staff will review the informed consent document with the subject. The subject will be provided information related to the study purpose, procedures, potential risks and benefits to participation, voluntary nature of their potential participation and provide them an opportunity to ask and have answers to all questions prior to obtaining any signature. A study investigator will be available to answer any questions. Subjects will not be compensated for participation and there are no additional costs to subjects for participation in the study.

Randomization Schema

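### ISSI, VAS and PGI-S are compared as unadjusted change and percent change from a baseline whose timing relative to surgery is not stated, which can cost precision and shrink the pain effect size the pilot is meant to deliver

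*Combined protocol and SAP*

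**What the plan says.** Study Methods puts consent before surgery ("Subjects will be screened and consented prior to their stent placement procedure for stone disease") and randomisation after it ("Patients will be formally enrolled and randomized post-operatively based on no severe complications intra-operatively"). Study drug starts on the day of stent placement. ISSI, AUASS, VAS and PGI-S are completed at baseline and at every follow-up. In the schedule of assessments these baseline scores fall under "Baseline/ Stent Placement", the same column as consent, screening laboratory tests, randomisation and study drug. No section says whether they come before or after the procedure.

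Inclusion criterion 2 admits two routes to a stent: "Subject scheduled to undergo a ureteral stent placement for ureteral obstruction or post-ureteroscopy procedure".

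Statistical Analyses plans, for the VAS: "Comparison of the change from baseline of total VAS between Myrbetriq™ and placebo will be made using an independent t test". The same t test on change is given for ISSI, a primary endpoint, and for PGI-S, with a chi-squared test for ordinal scoring. A general sentence adds chi-square and t tests to "compare percent change and mean change from baseline in the ISSI, voiding diary, narcotic log, VAS score and PGI-S". A split-plot ANOVA compares the arms over time. Covariance adjustment is mentioned only for the micturition and incontinence counts.

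Study Objective and Endpoints says of the pilot that "we will confirm the potential effect size for reduction in associated pain following stenting within this study population", and that its results will inform a larger study.

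**The concern.** The stent causes the symptoms that the drug is meant to relieve. A score taken before surgery describes the stone or the obstruction. A patient stented for painful obstruction may start high, and one with little pain before ureteroscopy may start near 0. The same stent pain then counts as improvement in one and worsening in the other. Subtracting such a baseline adds variation that says little about symptoms under the stent.

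Three things are at stake: the power of the ISSI, VAS and PGI-S comparisons, the standardised pain effect carried to the larger study, and the meaning of within-arm and percent change. A post-operative, pre-dose score would be a different quantity, and the plan as written allows either.

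**Working it through.** **The plan's own figure.** The only power statement is for ISSI: SD 4.17, 50 per arm, two-sided alpha 0.05, 80% power for a 25% difference. The detectable difference is 4.17 × √(2/50) × (1.960 + 0.842) = 2.34 points. That is 25% of a reference mean of 2.34/0.25, about 9.35. No mean is given, so the 80% can be neither confirmed nor refuted. Nor is it stated whether 4.17 is the SD of a score or of a change. No planning figure is given for VAS or PGI-S.

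**Is the contrast biased?** Stone relief and stent onset affect both randomised arms alike in expectation and cancel from the difference. In a simulation (20,000 trials per setting, 50 per arm, assumed SD 2, true effect −1, common shift −3, 0 or +3), the between-arm difference in change stayed between −0.995 and −1.003. The active arm's own change moved from −4.0 to −1.0 to +2.0. So the contrast is sound, and within-arm change is not a measure of drug benefit.

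**Precision, equal SDs.** SD(change) = SD × √(2(1 − ρ)); baseline-adjusted (ANCOVA) SD = SD × √(1 − ρ²). Take an effect with 80% power on the follow-up score (2.34/4.17 = 0.56 SD), 50 per arm. The values of ρ are assumed.

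| ρ | standardised effect on change | power, change | power, adjusted |
|---|---|---|---|
| 0 | 0.40 | 51% | 80% |
| 0.3 | 0.47 | 66% | 84% |
| 0.5 | 0.56 | 80% | 90% |
| 0.7 | 0.72 | 95% | 97% |

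**Precision with two indications (VAS).** All inputs are assumed: stented SD 2.5, baseline SD 2 within indication, half the patients per indication, baseline means g points apart, no indication gap once stented, within-indication correlation r, drug effect 1.4 points.

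Var(change) = (g/2)² + 2² + 2.5² − 2 × r × 2 × 2.5 = (g/2)² + 10.25 − 10r, against 2.5² = 6.25 for the stented score.

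The two are equal at r = [4 + (g/2)²]/10, which is 0.4 at g = 0, 0.5 at g = 2 and 0.8 at g = 4. At g = 6 the formula gives 1.3, so change is always the noisier measure.

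Power on the stented score is 79% (noncentral t, 50 per arm). At g = 2:

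| r | SD(change) | power, change | power, adjusted for baseline |
|---|---|---|---|
| 0 | √11.25 = 3.35 | 54% | 79% |
| 0.5 | √6.25 = 2.50 | 79% | 87% |
| 0.6 | √5.25 = 2.29 | 86% | 91% |

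At the unfavourable end (g = 6, r = 0), SD(change) is √19.25 = 4.39, the standardised effect is 2.5/4.39 = 57% of its stented-score value, and power is 35%. That depends on the indication gap vanishing under the stent. If half of it persists, the stented variance is 6.25 + 1.5² = 8.5 and the change variance is 1.5² + 10.25 − 10r. The ratio of SDs is then √(8.5/12.5) = 82% at r = 0 and √(8.5/9.5) = 95% at r = 0.3.

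**Percent change.** The denominator is the baseline score, so the quantity does not exist for a patient who scores 0.

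**The case against.** A reader might infer that stone relief contaminates the estimated drug effect. The planned tests do not support that, because they compare randomised arms. A reader might also assume that baseline is taken before surgery. The documents do not say so: randomisation is post-operative and shares the baseline column, so a post-operative, pre-dose score fits equally well. Nor is there an improved/not-improved split to criticise; the chi-squared test is named only for ordinal scoring.

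The precision loss is conditional. No correlation, VAS SD or indication gap is given, and above the break-even correlation change scores beat the raw follow-up score. The trial is an exploratory pilot with mainly descriptive efficacy analysis. Its summaries by treatment group and visit could supply stented-score means and SDs. The VAS endpoint is itself worded without reference to baseline: "Improvement in pain and discomfort perception using a 10 point Visual Analog Scale for pain assessment (VAS) at the 1 and 2 week follow-up".

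All of this stands, and it limits the point to precision and interpretation. It does not rescue the planned tests. The VAS test is on change although the endpoint is not, the split-plot ANOVA names no baseline covariate, and percent change is explicitly planned. Baseline adjustment does at least as well as either alternative in every case tabulated above, so the unknown correlation favours adjustment over change scores.

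**Conclusion.** The point holds as a matter of undefined baseline timing and unadjusted change scores, with no bias in the between-arm mean difference. If baseline reflects the stone or obstruction and its correlation with stented symptoms is below about 0.4 to 0.5 (assumed SDs, indication gap 0 to 2 points; higher for a larger gap), the planned VAS test loses power and the standardised pain effect shrinks. For example, power is 54% against 79% at zero correlation and a 2-point gap. Above that correlation the unadjusted change score is not worse than the raw score, though still below the adjusted analysis. These figures illustrate assumed inputs and do not forecast this trial. ISSI and PGI-S share the undefined timing and the unadjusted test, but the documents do not allow a size to be put on the loss for them.

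Two parts need no assumption about correlation: percent change is undefined at a baseline of 0, and within-arm change cannot be read as drug benefit. The VAS is exploratory, but its effect size is a declared aim of the pilot, so the plan should be changed.

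**What to change.** 1. State one fixed time, before the first dose, at which every patient completes the baseline questionnaires, and show it in the schedule relative to surgery.
2. For ISSI, VAS and PGI-S, replace the t test on change with the between-arm difference in the follow-up score at day 7 and at the stent removal/day 14 visit, adjusted for baseline score and stent indication. Use ANCOVA, or a repeated-measures model with baseline as covariate.
3. Report that difference with its confidence interval, and the SD of the stented score, as the pilot effect size for the larger study.
4. Delete percent change from baseline for these scales.

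The cost is mainly wording. The scores are already scheduled, the day 14 assessments already precede stent removal, and the indication is known at entry. If baseline is currently collected at varying times, fixing it also means a small change in procedure. Results will no longer read as simple improvement from baseline.
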